Subject exposures: Sequential subject study ID numbers will be randomized in 1:1 ratio to one of two experimental groups. Study drugs will be prepared daily by the research pharmacy and labeled only with the subject ID # and “study drug”. The patient, anesthesiologist, obstetricians, and research staff will remain blinded to assignment. All study subjects will receive standard care with prophylactic oxytocin bolus and infusion, as well as second-line uterotronics on an as-needed basis per institutional protocol. (**Appendix 2**)

- Calcium: 1 gram CaCl₂ in total volume 60mL delivered over 10 minutes beginning 2 minutes after fetal delivery.
- Placebo: 60mL sterile saline delivered over 10 minutes beginning 2 minutes after fetal delivery

Outcomes and Measurement: The primary outcome will be quantitative blood loss (QBL) in mL, which is calculated by standardized methodology including volumetric (suction cannister contents after subtracting amniotic fluid volume) and gravimetric (weighing soiled surgical sponges, drapes, and pads) assessment. Secondary outcomes will include the following: uterine tone assessments by the obstetric attending on a validated 10-point numerical rating scale¹⁴ (NRS_{UT}) at study drug initiation 2 minutes after fetal delivery and reassessed every 5 minutes thereafter until fascial closure. Additionally, total oxytocin bolus and infusion doses, second line uterotronics, change in hematocrit from preoperative to postoperative day one values, total intravenous fluids, and a composite outcome indicating hemorrhage morbidity including transfusion during the hospital stay, hysterectomy, uterine artery embolization, intensive care admission, and death will be recorded.

Please see Appendix 3 for forms to be filled out by research staff.

Data Analysis: Analyses will be conducted using R and supervised by a biostatistical consultant from the Stanford Quantitative Sciences unit. Continuous data will be represented using mean (\pm SD) or median (interquartile range) for variables not normally distributed and compared using parametric or non-parametric t-tests as appropriate. Categorical data will be presented using proportions and compared using a chi-square (or Fishers Exact) test. Two-sided p-values less than 0.05 will be considered statistically significant.

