We anticipate a two-compartment mammillary model with an effect site. Calcium is administered into the central compartment, also the site of drug sampling. Calcium is also eliminated from the plasma compartment. Calcium may distribute from the plasma compartment to one or more compartments. Drug effect is mediated by the concentration in a hypothetical "effect site", in this case the uterus¹⁷. The effect site permits modeling of hysteresis between the time course of plasma calcium concentration increase and increase in uterine tone measured in Aim 1. PK modeling will be done in the volume and clearance domain and include the influence (if any) of age, weight, gestational age, pH, starting hematocrit, and blood loss.

Equation 1 is an equation for the sigmoidal PD model. Because the measure of drug effect is the NRS_{UT} is an ordinal measure, it will be dichotomized into 4 categories, 0-3, 4-10, 7-10, and 9-10, and modeled as the probability of being in each category as shown in **Figure 2**. PD models will be estimate p_0 , p_{MAX} , C_{e50} , and γ (the baseline probability of uterine tone X, the maximum probability of uterine tone X, the concentration associated with 50% of the change in probability, and the steepness of the concentration versus probability relationship). The effect of pH and uterotonics including oxytocin, methylergonovine, and carboprost on the PD parameters will be explored.

$$p(NRS_{UT} \leq X) = p_0 + (p_{MAX} - p_0) \frac{Ce^{\lambda}}{Ce^{\gamma} + Ce^{\lambda}}$$

Figure 2. PD models will be estimate p_0 , p_{MAX} , C_{e50} , and γ (the baseline probability of uterine tone X, the maximum probability of uterine tone X, the concentration associated with 50% of the change in probability, and the steepness of the concentration versus probability relationship). The effect of pH and uterotonics including oxytocin, methylergonovine, and carboprost on the PD parameters will be explored.

Equation 1: Pharmacodynamic model for the probability of uterine NRS and calcium concentration

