Appendix 2: Stanford Labor and Delivery protocol for intrapartum cesarean delivery

Monitoring: All patients undergoing intrapartum cesarean delivery are monitored by continuous pulse oximetry, 3-lead EKG, and noninvasive blood pressure oscillometry. Blood pressures are obtained every 1 minutes prior to fetal delivery. For clinically stable patients at the discretion of the anesthesia team, blood pressure frequency may be decreased to every 2.5-5 minutes after fetal delivery.

Antibiotics:

- Patients without antibiotic allergy or chorioamnionitis receive 2 grams intravenous cefazolin (3 grams if >120 kg) prior to incision and 500 mg of intravenous azithromycin over a one-hour infusion for endometritis prophylaxis.
- Patients with a clinical diagnosis of chorioamnionitis instead receive intravenous ampicillin 2g, gentamycin 5 mg/kg over a one-hour infusion, and clindamycin 900 mg intravenously

Neuraxial anesthesia:

- Patients with a labor epidural in situ receive epidural top-up with divided doses of 2% lidocaine with epinephrine 1:200,000 to achieve a T4 dermatomal level to pinprick bilaterally (generally 15-25 mL total volume). 100 mcg epidural fentanyl is added at the discretion of the attending anesthesiologist. All patients receive 3 mg epidural morphine prior to case conclusion for postoperative analgesia.
- Patients without a labor epidural in situ receive a single-shot spinal or combined spinal-epidural anesthetic, with a standard intrathecal medication cocktail of 1.6 mL 0.75% hyperbaric bupivacaine, 15 mcg fentanyl, and 100 mcg morphine.

Uterine tone assessment and uterotonic medications:

- At the time of fetal delivery, 2 units of intravenous oxytocin are administered, and an oxytocin infusion is initiated at 7.5 units/hr
- 2 minutes after fetal delivery, the uterine tone is assessed by palpation of the uterine fundus and rated on a scale from 0-10, with 0 representing a completely atonic uterus and 10 representing a firm and completely contracted uterus. This score is recorded. For uterine tone score <8/10, an additional 2 units oxytocin are administered, and oxytocin infusion increases to 15 units per hour

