- 7 minutes after fetal delivery, uterine tone is again assessed by palpation and score recorded. For scores <8/10, oxytocin 2 units are administered for a 3rd time, oxytocin infusion increases to 30 units/hr, and the anesthesia and obstetric teams discuss whether a second line uterotonic may be warranted. If so, the anesthesia team begins preparation of the second line uterotonic agent. This agent is administered if uterine tone is still deemed inadequate at the discretion of the anesthesia and obstetric teams.
- 12 minutes after delivery, uterine tone is again assessed by palpation and score recorded. For scores <8/10, the obstetric and anesthesia teams will discuss whether a second line uterotonic may be clinically indicated.
- The uterotonic protocol outlined can be changed based on clinical picture or obstetrician request.

Quantitative blood loss:

Quantitative blood loss (QBL) is measured for all cesarean deliveries by a standardized protocol. The protocol follows nationally recommended methodology that combines gravimetric (measurement of suction cannister contents after subtraction of the amniotic fluid volume) and volumetric (weighing all surgical sponge and drape and subtracting dry weights) QBL.^{1,2} This process is performed by the clinical labor and delivery nurses, all of whom receive standardized training in performing the technique.

1. Quantitative Blood Loss in Obstetric Hemorrhage: ACOG COMMITTEE OPINION, Number 794. *Obstetrics and gynecology* 2019;134(6):e150-e156.

Appendix 3 Protocol Sheet: CALCIUM CHLORIDE FOR PREVENTION AND TREATMENT OF BLOOD LOSS FROM UTERINE ATONY DURING INTRAPARTUM CESAREAN DELIVERY

STUDY ID NUMBER (on study drug syringe): _____

Reminder: This study investigates whether one gram of calcium chloride IV, administered over 10 minutes starting 2 minutes after fetal delivery, decreases blood loss from uterine atony during intrapartum cesarean.

- Primary outcome: Quantitative Blood Loss
- Secondary outcomes: Uterine tone scores, uterotronics, side effects

Please confirm inclusions with a checkmark or X:

- Patient is 18-55 years old
- Patient is having an intrapartum cesarean delivery

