- Patient received oxytocin infusion for labor induction or augmentation.
- Patient still wants to participate and has signed consents

Please confirm this patient has NO EXCLUSIONS:

- Patient does not have renal dysfunction with serum Cr>1.0 mg/dL
- Patient does not have any known cardiac conditions
- Patient is not receiving a calcium channel blocker (none in last 24 hours)
- Patient is not receiving digoxin for a maternal or fetal indication
- This is not an emergency in which participation in the study could hinder or delay care

Study drug:

- The syringe contains **60mL saline with 1-gram Calcium Chloride OR 60mL saline placebo**
- Administer via syringe pump and microbore tubing over 10 minutes
 - Program a basic infusion on Alaris pump for basic infusion, **360mL/hr**
 - Attach microbore tubing to injection port closest to the patient
 - Start infusion **2 minutes after fetal delivery** (1 minute after cord clamp)
- Assume that every infusion contains 1 gram of calcium and **discontinue** if concerns for extravasation (arm pain and redness or signs of infiltration), hemodynamic compromise (bradycardia and hypotension most common). Contact [name] via email or cell [contact] for any concerns and document on next page.

PLEASE FILL OUT ALL INFORMATION ON THE NEXT PAGE.

STUDY ID NUMBER (on study drug syringe): _____

USE EPIC COMPUTER CLOCK FOR ALL TIMES

Fetal Delivery and oxytocin 2 unit bolus :

Time: _____

2 minutes after fetal delivery:

• Ask obstetrician to rate uterine tone 0-10: Tone: _____

• Start study drug infusion: Time Started: _____

• *If infusion was paused or stopped* Time paused: _____

Time restarted: _____

7 minutes after fetal delivery:

• Ask obstetrician to rate uterine tone 0-10: Tone: _____

12 minutes after fetal delivery:

• Ask obstetrician to rate uterine tone 0-10: Tone: _____

19 minutes after fetal delivery:

• Ask obstetrician to rate uterine tone 0-10: Tone: _____

Side effects (did the patient experience any of the following possibly related to the study drug? Circle Yes/No)

- Arm or IV site discomfort? YES / NO
- Concern for extravasation? YES / NO
- Heart rate change or arrhythmia? YES / NO Describe: _____
- Hypertension or hypotension YES / NO Describe: _____
- Flushing YES / NO
- Abnormal sensations or tastes YES / NO Describe: _____
- Nausea YES / NO
- Vomiting YES / NO
- Other YES / NO Describe: _____

Was the infusion started exactly 2 minutes after fetal delivery? YES / NO

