If not, please explain why: _____

Was the whole infusion given? If not or if paused, please explain why below

STUDY ID NUMBER (on study drug syringe): _____

If patient consents to up to 6 lab draws of 0.5mL venous blood:

- Research staff (fellow or research assistant) to analyze samples in a **different operating room**.
- **DO NOT** participate in patient care or converse with staff or the patient in the delivery room other than to obtain permission to obtain blood samples, as your knowledge of these lab values could compromise blinding of the patient, anesthesiologist, or obstetrician.

Times to target for blood samples relative to the start of study drug infusion:

• Baseline (prior to study drug start)	• 10-30 minutes
• 0-5 minutes	• 30-60 minutes
• 5-10 minutes	• 60-240 minutes

Carefully document the time that the blood was drawn using **EPIC computer clock** for each sample.

Use the **research iSTAT machine** and research EG7+ cartridges.

For patient ID on the iSTAT, please enter the study ID number and not the MRN

Time study drug started: _____

Baseline: Time: _____ pH: _____

iCa: _____

Sample 2: Time: _____ pH: _____

iCa: _____

Sample 3: Time: _____ pH: _____

iCa: _____

Sample 4: Time: _____ pH: _____

iCa: _____

Sample 5: Time: _____ pH: _____

iCa: _____

Sample 6: Time: _____ pH: _____

iCa: _____

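### The bedside form records no clock time for any uterine tone score, so the Aim 2 calcium-to-tone lag rests on times that cannot be verified or corrected if scores run late

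*Combined protocol and SAP*

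**What the plan says.** Under Outcomes and Measurement (Specific Aim 1), tone is scored "at study drug initiation 2 minutes after fetal delivery and reassessed every 5 minutes thereafter until fascial closure". The infusion is described under Subject exposures as "1 gram CaCl₂ in total volume 60mL delivered over 10 minutes beginning 2 minutes after fetal delivery". The protocol text thus treats study-drug start and 2 minutes after delivery as the same moment.

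Appendix 2, the institutional protocol, counts from delivery: "2 minutes after fetal delivery, the uterine tone is assessed by palpation of the uterine fundus and rated on a scale from 0-10", then "7 minutes after fetal delivery, uterine tone is again assessed by palpation and score recorded", then again at 12 minutes. The Appendix 3 data page uses the same clock, with rows at 2, 7, 12 and 19 minutes after delivery.

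That page has time blanks for delivery, infusion start, pause and restart, and it names the hospital computer clock for all times. It also asks "Was the infusion started exactly 2 minutes after fetal delivery? YES / NO" and wants a reason if not. For blood samples the instruction is "Carefully document the time that the blood was drawn using" that clock, with a time blank for each sample. The four tone rows have a blank for the score and none for the time.

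Under the Aim 2 pharmacokinetic and pharmacodynamic analysis, the scores are used as follows: "The effect site permits modeling of hysteresis between the time course of plasma calcium concentration increase and increase in uterine tone measured in Aim 1". Nothing states whether that model uses nominal or actual score times.

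**The concern.** A lag between two curves can be estimated only if both are placed correctly in time. Here the calcium side carries recorded times and the tone side carries row labels. The infusion lasts 10 minutes and spans the 7- and 12-minute scores, so an error of a minute or two is not small against the signal.

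Two gaps follow:

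- A score taken late leaves no trace of its lateness.
- If the infusion starts late, a score in the 7-minute row may have been taken 7 minutes after delivery (the form and Appendix 2) or 5 minutes after drug start (one reading of the Aim 1 text). The form cannot show which.

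At stake is the effect-site rate in Aim 2. Times not written down at the bedside cannot be rebuilt from this form.

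**Working it through.** The plan states no figure for this point, so there is nothing to reproduce. The check has two parts.

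**1. The time grids**

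- Aim 1 text, every 5 minutes from minute 2: 2, 7, 12, 17, 22 and so on after delivery.
- Form: 2, 7, 12, 19, with no later row.
- With an on-time infusion the two agree at 2, 7 and 12 minutes. The 17-versus-19 difference and the missing later rows are a separate schedule question.
- With an infusion *d* minutes late and scores kept on the form's clock, time since drug start = labelled minute − (recorded start − recorded delivery). Both times are on the form, so *d* is recoverable.
- With a score *e* minutes late, *e* is not recoverable.

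**2. Illustrative size**

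Inputs:

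- Table 2 pilot values Cl₁ = 0.93 and V₁ = 75.6. Units are not given; minutes are assumed. Then k = 0.93/75.6 = 0.0123 per minute.
- A 10-minute infusion.
- Scores at 0, 5, 10 and 17 minutes after drug start (the form's minutes less 2).
- Assumed true effect-site rates (ke0) of 0.2 and 0.1 per minute, and assumed lateness of 1 to 3 minutes. The documents give neither.

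Model:

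- During infusion Cp(t) ∝ (1 − e^(−kt))/k; afterwards Cp decays at rate k.
- dCe/dt = ke0 × (Cp − Ce).
- Tone effect = slope × Ce, without noise. ke0 and the slope are refitted by least squares.

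| Situation | True ke0 0.2 fitted as | True ke0 0.1 fitted as |
|---|---|---|
| All on time | 0.2 | 0.1 |
| Every score 1, 2, 3 min late, nominal times used | 0.315, 0.480, 0.805 | 0.168, 0.245, 0.343 |
| Infusion late, form clock kept, recorded times used | 0.2 | 0.1 |
| Infusion 1, 2 min late, lateness ignored | 0.110, 0.038 | not tabulated |
| Infusion 1, 2 min late, scores held to drug start, then corrected as if on the delivery clock | 0.34, 0.69 | 0.18, 0.34 |

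As half-times (ln 2/ke0), a true 0.693/0.2 = 3.5 minutes becomes 0.693/0.315 = 2.2, 0.693/0.480 = 1.4 and 0.693/0.805 = 0.9 minutes in the second row.

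Sensitivity:

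- If a baseline is also fitted and all scores are late, a true 0.2 becomes 0.30 to 0.58 over 1 to 3 minutes.
- Zero-mean timing scatter of up to ±2 minutes gives 0.201, essentially no bias.
- With the slope held fixed, a true half-time of 5 minutes is fitted as about 4.2, 3.4 and 2.6 minutes for scores 1, 2 and 3 minutes late. Raising k to 0.1 per minute changes these only to about 4.2, 3.5 and 2.8, so the assumed time unit is not what drives the result.

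**The case against.** **The two anchors do not contradict each other.** The Aim 1 phrase names them as one moment, and Appendices 2 and 3 both count from delivery. They separate only after an off-schedule start. This stands. What remains is that the form foresees such starts and no section says which anchor then governs.

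**A late infusion is already covered.** A reader might infer that any late start puts tone on the wrong time axis. The documents do not support that: delivery, start, pause and restart times are all recorded, and if scores follow the form's labels the correction is exact. It fails only if staff hold scores until drug start and enter them under delivery-based headings. Nothing shows that they do, but nothing on the form would reveal it.

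**The bias figures depend on assumptions.** This also stands. The large values need every score to be late by the same amount, in a linear, noise-free model. The plan specifies a sigmoid model for tone categories with an estimated baseline, and no document gives any lateness. A reader might also infer that the lag will be underestimated. The direction is not fixed: late scores shorten the apparent lag, and an ignored late infusion lengthens it.

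**Aim 1 is not harmed.** A reader might infer that late starts distort the tone comparison between arms. Having less drug on board after a late start is a real difference in exposure, not a measurement error, and a time field would not change it. Staff are blinded, so delays have no evident reason to differ by arm, and scores at the same minute after delivery give a valid randomised contrast.

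**The hospital record may time-stamp the scores.** The documents do not say, and the plan should not depend on it.

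**Conclusion.** The point holds in a limited form. The tone scores are the only timed observations in the lag model without a recorded time, and an unrecorded late score cannot be corrected from the form. After a late start, the form also leaves the anchor for the scores unknown.

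The size is conditional. It is nil with exact timing, nil for a late start on the delivery clock with recorded times used, and close to nil with zero-mean scatter. Under uniform lateness of 1 to 3 minutes the fitted rate is roughly 1.6 to 4 times the truth (0.315/0.2 to 0.805/0.2). With a 1-minute-late infusion ignored it is about half (0.110/0.2). These figures illustrate what could happen; they do not predict this trial.

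The consequence is confined to the Aim 2 pharmacodynamic model. The primary blood loss comparison, its sample size and the randomised tone comparison are not invalidated. This is a cheap improvement to data collection.

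**What to change.** - In Appendix 3, add a time blank beside each of the four tone scores, on the hospital computer clock already used for the infusion and blood samples.
- In the Aim 2 analysis section, state that the pharmacodynamic model uses each score's actual time relative to the actual infusion start, allowing for pauses.
- Reconcile Outcomes and Measurement with Appendix 3 so that one anchor for the scores is stated, including what happens to the scores when the infusion starts late. The 17-versus-19-minute row and the absence of later rows can be settled in the same edit.

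The cost is four blanks, two or three sentences, and a few seconds of recording per score by staff who already log times on that clock. No extra patients, procedures or staff are needed.

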As part of the pilot RCT, we also gathered serial serum venous blood samples from a subset of participants. This was done for two main purposes: 1) to ensure a reliable but safe rise in ionized calcium from the 1-gram dose of CaCl₂, and 2) to generate sample size calculations for a definitive study of CaCl₂ PK in a similar pregnant patient cohort. Data and a 1-compartment PK model are shown in **Figure 1**. As anticipated, a rapid and reliable and safe-level peak in ionized calcium was obtained in subjects who received CaCl₂.

EXPERIMENTAL DESIGN AND METHODS

SPECIFIC AIM 1 OVERVIEW: Based on our preliminary data, we propose a double-blind, placebo-controlled, 120-patient RCT to assess the effect of prophylactic CaCl₂ infusion upon blood loss and uterine tone at the time of intrapartum cesarean delivery. Patients will be randomly assigned to receive a prophylactic infusion containing one gram of dilute CaCl₂ or saline placebo in addition to standard of care oxytocin after fetal delivery. We will assess quantitative blood loss and serial measurements of uterine tone.

Study population: The study will enroll adult pregnant patients age 18-45 years of age at >34 weeks gestation who require intrapartum cesarean delivery and have received an exogenous oxytocin infusion for labor induction or augmentation, as these are known risk factors for uterine atony^{1,2}. Exclusions include emergent surgery, known cardiac dysfunction, renal dysfunction with serum Cr >1.0, hypertension necessitating intravenous hydralazine or labetalol during labor, and treatment with calcium channel blockers or digoxin.

Subject enrollment: All laboring patients on the unit receive a brief informational handout about this study upon admission (**Appendix 1**). Research staff visit all laboring patients twice daily after permission to approach and introduction by the bedside nurse, once in the morning and once in the afternoon, to obtain informed consent from all willing laboring patients if they require cesarean delivery. Consent and study inclusions/exclusions are confirmed by the clinical anesthesiologist at the time of decision by the obstetrics team to proceed with an intrapartum cesarean delivery.

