Analysis of Primary Aim: The primary outcome of the study is the difference in quantitative blood loss between the two groups on an intention-to-treat basis. Patients who are found to have non-atomic reasons for blood loss including morbidly adherent placenta, hysterotomy extension, cervical, or vaginal lacerations will be included in primary outcome assessment. The trial is also powered for planned subgroup analysis excluding these cases. In addition, subgroup analyses based upon risk factors for atony including chorioamnionitis, total oxytocin exposure, indication for cesarean, magnesium infusion, and preeclampsia will be performed.

Sample size: Power analysis of the data from our pilot RCT revealed that a sample size of 31 patients per arm will have 90% power to detect a difference of 200mL in quantitative blood loss between groups at the $p<0.05$ significance level. The sample size was increased to 60 patients per arm to allow sufficient power for the planned subgroup analysis excluding patients with non-atomic etiologies of blood loss which may occur in up to 40% of cases. This same sample size will also generate 86% power to detect a rank test difference of 2 points in the ordinal secondary outcome measure of NRS_{UT} . We anticipate signing consent documents with approximately 1200 laboring patients to obtain the 120 subjects who meet enrollment criteria, as most of these patients will have normal spontaneous vaginal delivery, some may later decline to participate, some may develop exclusions such as renal dysfunction, and some may require stat delivery without time to safely administer the study medications in addition to standard care.

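### Total oxytocin dose is compared without adjusting for the 2-minute tone score that sets part of it before calcium can act; this costs precision but does not cause bias

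*Combined protocol and SAP*

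**What the plan says.** - **Outcome.** Outcomes and Measurement (Specific Aim 1) lists "total oxytocin bolus and infusion doses" among the secondary outcomes, with no start time, end time or split. Data Analysis provides parametric or non-parametric two-group tests and no stratification or covariate.
- **Study drug.** Subject exposures has it "delivered over 10 minutes beginning 2 minutes after fetal delivery".
- **Oxytocin at delivery.** Appendix 2: "At the time of fetal delivery, 2 units of intravenous oxytocin are administered, and an oxytocin infusion is initiated at 7.5 units/hr".
- **Oxytocin at 2 minutes.** Appendix 2: "For uterine tone score <8/10, an additional 2 units oxytocin are administered, and oxytocin infusion increases to 15 units per hour". Outcomes and Measurement times the first tone score "at study drug initiation 2 minutes after fetal delivery and reassessed every 5 minutes thereafter until fascial closure". The Appendix 3 form has a space for it, placed just before the line for starting the infusion.
- **Oxytocin at 7 minutes.** Appendix 2 gives a third 2-unit bolus and a rate of 30 units/hr if tone is below 8. This is the first scheduled step after study-drug exposure begins.
- **Subgroups.** Analysis of Primary Aim plans subgroup analyses on "risk factors for atony including chorioamnionitis, total oxytocin exposure, indication for cesarean, magnesium infusion, and preeclampsia", with no time window for the oxytocin item.

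**The concern.** A dose decided before calcium can act carries no information about calcium. Adding it to the outcome leaves the expected difference between arms unchanged but raises the variance. It also lets a chance imbalance in 2-minute tone pass straight into the oxytocin comparison. What is at stake is the ability of this secondary outcome to show an oxytocin-sparing effect if there is one.

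A lesser issue is that the subgroup factor also refers to total oxytocin, without a window. If intraoperative doses were counted, patients would be grouped by a response that follows randomisation and is itself a listed outcome.

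**Working it through.** The plan states no power or precision figure for the oxytocin outcome, so there is none to reproduce.

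**1. What is fixed before calcium can act (Appendix 2 followed strictly, through the 7-minute step).** Write total bolus as T = 2 + A + B. A is 2 units if 2-minute tone is <8 and otherwise 0. B is 2 units if 7-minute tone is <8 and otherwise 0. Only B can respond to calcium.

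| Tone at 2 min | Tone at 7 min | Total bolus (units) | Fixed part, 2 + A | Share fixed |
|---|---|---|---|---|
| >=8 | >=8 | 2 | 2 | 100% |
| >=8 | <8 | 4 | 2 | 50% |
| <8 | >=8 | 4 | 4 | 100% |
| <8 | <8 | 6 | 4 | 67% |

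For the infusion, 7.5 x 2/60 = 0.25 units run before study drug. From 2 to 7 minutes the amount is 7.5 x 5/60 = 0.625 or 15 x 5/60 = 1.25 units, depending only on the 2-minute score.

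**2. Mean and variance.** The constant 2 cancels between arms, and A has the same expectation in both by randomisation. The expected difference in T therefore equals that in B. An illustrative simulation (mean tone 7.5 at 2 minutes, calcium +1 point at 7 minutes, both assumed) shows this:
- Total bolus: 3.692 - 4.151 = -0.459 units, SD 1.564.
- B alone: 0.442 - 0.899 = -0.457 units, SD 0.944.
- Variance removed: 1 - 0.944²/1.564² = 1 - 0.891/2.446 = about 64%.

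**3. Power.** Assumptions: 60 per arm; mean 2-minute tone 7 to 8.75; between-patient SD 1.3 and within-patient SD 0.8; calcium +1 to +1.5 points at full dose and half of that at 7 minutes; strict Appendix 2 titration; two-sided 5% level.

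| Rank test on | Unstratified | Stratified by 2-minute tone |
|---|---|---|
| Total bolus dose | 9-26% | 26-69% |
| Infusion dose | 10-32% | 26-69% |

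Type I error was 4-6%.

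**4. Why stratification is enough.** Within a 2-minute stratum, 2 + A is constant, so ranking patients on T or on B gives the same order. The early infusion amounts are constant within a stratum too. Under the strict schedule, the stratified test therefore gives the same result with or without removing the pre-drug dose.

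**5. Subgroup factor.** Study population requires that patients "have received an exogenous oxytocin infusion for labor induction or augmentation, as these are known risk factors for uterine atony". Analysis of Primary Aim then lists oxytocin exposure as a risk factor beside chorioamnionitis, indication for cesarean, magnesium and preeclampsia. Together these point to labor oxytocin.

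If intraoperative doses were counted instead, an assumed constant effect of -100 mL on blood loss appeared as -82, -65 and -56 mL in patients with 2, 4 and 6 bolus units (same simulation as step 2). It stayed at -100 mL in both strata of the 2-minute score. One clause in the plan would rule out this reading.

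**The case against.** The strongest reply is that this is a matter of efficiency and not an error. The arms are randomised, the unadjusted comparison is valid, total dose is a meaningful quantity, and it matches the row in the pilot's Table 1. The plan powers only blood loss and the tone score, so oxytocin dose is an unpowered secondary outcome either way. All of that stands. A reader might infer that the outcome is biased; it is not, since the fixed dose cancels and the rest is balanced in expectation.

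The tone inputs are assumed, and Appendix 2 lets the uterotonic protocol change with the clinical picture or at the obstetrician's request. That also stands, so the power figures show direction and rough size only. The gain does persist at a mean tone of 8.75, which is nearer the pilot. It is not confined to boluses, as the infusion row shows.

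Three stronger readings are tempting, and the documents do not support them:
- **That the subgroup analysis conditions on a treatment response.** The wording permits it, but its context points to labor oxytocin.
- **That the pilot's oxytocin trend is a product of the pre-drug bolus.** Placebo patients in the pilot had a median bolus of 2 units with a median maximal rate of 15 units/hr. Under strict Appendix 2 titration any rate above 7.5 comes with a second bolus, so the pilot does not fit that schedule and the inference fails.
- **That dose times are already available for a split.** The documents do not say so. The Appendix 3 form has no field for later boluses, rates or totals.

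**Conclusion.** The point holds as a loss of precision in one secondary outcome. Under Appendix 2 the delivery dose is the same for everyone, and the 2-minute step is set by tone scored at study-drug start. An unadjusted comparison of totals therefore includes variation that calcium cannot influence. On the assumptions above, stratifying by that score raises power for total bolus from about 9-26% to 26-69%, with type I error near 5%. Even then the outcome is well powered only in the more favorable scenarios. The size of the gain depends on the assumed tone distribution and effect, and on how closely clinicians follow the schedule. The primary analysis is untouched. The subgroup wording needs only a clarification of its likely intent.

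**What to change.** 1. In Data Analysis, state that oxytocin bolus and infusion doses will each be compared by a rank test (van Elteren) stratified by the 2-minute tone score, <8 or >=8.
2. If dose times are available, count doses from study-drug start to fascial closure, treating the step triggered by the 2-minute score as pre-drug. Starting the count at the 7-minute assessment would instead lose any off-schedule dose given between 2 and 7 minutes. Dose times are not essential, because under the strict schedule the stratified test gives the same result without them.
3. In Analysis of Primary Aim, define the oxytocin subgroup factor as labor oxytocin given before fetal delivery.

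The cost is a few sentences. The stratifying score is already on the Appendix 3 form, and clinical care does not change. The small downside is that the stratified result is not directly comparable with the pilot's total-dose row; unadjusted totals can still be reported descriptively.
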